#### **4.2 Outcome**

The outcomes can be classified as those related to the effectiveness of the AI support at the time of CXR acquisition for immediate review (immediate report and straight to CT where appropriate; Part A) and those related to the health economic assessment [Part B]. A discrete choice experiment will be conducted to inform the health economic analysis, led by University College London (UCL) health economists [Part C] and will be reviewed by UCL ethics. Patient experience and communication preferences [Part D] and staff engagement [Part E] are components of the larger programme of work and independent evaluation, performed in partnership with UCLPartners and City University. City University ethical approval is already in place for the staff engagement [Part E reference ETH2223-0030 and will be applied for [Part D]. Workstreams C-E are part of the larger programme and are outside the scope of this protocol.

Outcomes related to clinical evaluation [Part A]

The primary outcomes related to clinical evaluation (Part A) are:

A1. The difference in time (in days) to the diagnosis of lung cancer for patients who have CXRs with an AI support at the time of CXR acquisition and prioritisation for immediate review and those that have no immediate read but the AI read is available at the time of reporting.

A2. The difference in time (in days) to CT for patients with suspected lung cancer who have CXRs with an AI support at the time of CXR acquisition and prioritisation for immediate review and those that have no immediate read but the AI read is available at the time of reporting.

Rationale for choice of two primary outcomes:

A strength of the trial is the multisite, pragmatic design of the clinical evaluation. Pre-trial review has demonstrated heterogeneity in radiology workflows (CT scanner capacity, community sites without CT on-site, CT reporting times), referral routes and lung cancer pathway design (respiratory review prior to CT, virtual triage) at the clinical sites. Time to lung cancer diagnosis is clinically meaningful and time to CT will be the least affected by the heterogeneity inherent in this study. Both outcomes will be considered primary and there are no hierarchy among these two. A sub-group analysis will be undertaken for these endpoints by sites and time periods (quarterly interval).

Other steps in the patient pathway for the diagnosis of lung cancer are included as secondary outcomes. The secondary outcomes are:

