### 7.3.1 Size of sample

#### Part A

The primary endpoints of this study are the difference in median time between CXRs suspicious for lung cancer and CT chest and the difference in median time to lung cancer diagnosis between routine reporting with AI available and AI support at the time of CXR acquisition and prioritisation for immediate review of CXRs reporting arms. The expected prevalence of lung cancer in this cohort (primary care referrals for CXR) is 0.6%. Thus for 150,000 CXRs this will lead to the detection of about 900 cancer cases. Using data from previous work, the median time to lung cancer diagnosis was 63 days in the standard reporting group and if we use a conservative reduction of 10 days, with 95% power we would need 265 cases per group (Table 6). Most likely, the time to diagnosis is going to be greater than 10 days such that the sample size will give us plenty of power to detect a difference between the groups on time to diagnosis. Considering that 30% of lung cancer patients die within 90 days of diagnosis, a 10 or more-day difference is clinically significant (Table 7).

The co-primary endpoint of this study is time between an abnormal CXR that is suspicious for lung cancer to CT chest. Based on the NHS Diagnostic Imaging Dataset between 4,000-4,500 CT chest scans referred from primary care are expected during the study period at the clinical sites, median time for England (CT chest request to test) is 14 days, but this data is not segregated between urgent scans and those that are routine or for follow up. The mean and standard deviation of time between abnormal CXR and CT chest are not known for either the intervention (AI support at the time of CXR acquisition and prioritisation for immediate review of CXRs) or routine CXR reporting with AI available. Cohen's d (effect size) was used to estimate sample size with power 0.1, 0.3 and 0.5 are considered small, moderate and large effect size. Assuming approximately equal distribution (Nnotification:Nstandard as 0.8 to 1.2) of the number of scans taken, the estimated 4,000 CT chest scans will give adequate power to detect even the smallest effect size (Cohen's d = 0.1; Figure 2). We have defined a clinically meaningful difference in time from abnormal to CT chest as 3 days, using the maximum time recommended in the NOLCP.

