**Figure 2. Sample size calculation for time from abnormal CXR to CT chest (days)**

We would also like to have enough numbers to examine the secondary outcome if the strength of the agreement between qXR and CXR reporter in normal/abnormal classification. Based on an anticipated abnormal prevalence 40% of primary care CXRs and as measured by kappa (hypothesized as 0.82) an absolute precision of 2%, we would need 3,601 patients included. Not only is the time to diagnosis is important but also the accuracy of diagnosis. The study will also have enough number to report on agreement of individual abnormality with the above precision.

Table 7. Sample size calculation for time (in days) to diagnosis of lung cancer

	Median Days to diagnosis	Hazard	Sample Size	Total sample size	POWER
Routine	38	0.018	201	402	90
qXR immediate	28	0.025			
Routine	32	0.022	156	312	90
qXR immediate	22	0.032			
Routine	63	0.011	759	1518	90
qXR immediate	53	0.013			
Routine	63	0.011	567	1134	80
qXR immediate	53	0.013			
Routine	20	0.035	51	102	90
qXR immediate	10	0.0693			

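### The claim of 95% power from 265 lung cancers per group for 63 versus 53 days contradicts the protocol's own Table 7; the roughly 900 cancers expected give about 70–73%

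*Protocol*

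**What the plan says.** Section 7.3.1 (Part A) bases the sample size for primary outcome A1, time to diagnosis of lung cancer, on an earlier single-site trial in which "the median time to lung cancer diagnosis was 63 days in the standard reporting group". It continues "if we use a conservative reduction of 10 days", and then "with 95% power we would need 265 cases per group (Table 6").

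On the number available, with 0.6% prevalence: "Thus for 150,000 CXRs this will lead to the detection of about 900 cancer cases". The paragraph expects the true reduction to exceed 10 days and concludes that "the sample size will give us plenty of power to detect a difference between the groups on time to diagnosis". It also calls a difference of 10 days or more clinically significant.

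The supporting table is headed "Table 7. Sample size calculation for time (in days) to diagnosis of lung cancer". Its first 63 versus 53 day entry has a routine-arm line ending "0.011 759 1518 90", that is, hazard 0.011, 759 per group, 1,518 in total, 90% power. A second entry for the same medians gives 567 per group and 1,134 in total for 80%. The other three entries, all for 90% power, are also 10-day reductions, from lower baselines: 38 to 28 days (201 per group), 32 to 22 (156) and 20 to 10 (51).

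**The concern.** The text and the table address the same comparison, 63 versus 53 days, and give incompatible answers. The text claims higher power (95% against 90%) from about a third of the cases (265/759 = 0.35). No row of Table 7 shows 265 cases or 95% power, and the table cited in the sentence contains no sample-size figures, so 265 has no visible source.

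This matters because 900 expected cancers look ample beside 2 × 265 = 530, but fall short of both 1,134 and 1,518. A reader of the text would believe that the trial is comfortably powered for the reduction that it calls both conservative and clinically significant. A reader of Table 7 would see that it does not reach 80% for that reduction. The stated power also bears on how a non-significant result for A1 would be interpreted.

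**Working it through.** **Inputs.** Medians of 63 and 53 days (section 7.3.1 and Table 7); printed hazards 0.011 and 0.013 (Table 7); 150,000 × 0.006 = 900 cancers, taken as 450 per arm. The protocol states no alpha for this calculation. Two-sided 5% is assumed because it reproduces Table 7, as step 1 shows.

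**Step 1: reproduce Table 7.** For exponential times, equal groups and every case an event, with hazards λ₁ and λ₂ and mean hazard λ̄:

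n per group = [1.96 × √2 × λ̄ + z_power × √(λ₁² + λ₂²)]² / (λ₁ − λ₂)²

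For 0.011 and 0.013: λ̄ = 0.012, 1.96 × √2 × 0.012 = 0.03326, √(λ₁² + λ₂²) = 0.01703, difference 0.002.

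- 90%: (0.03326 + 1.2816 × 0.01703)² / 0.002² = 758.6
- 80%: (0.03326 + 0.8416 × 0.01703)² / 0.002² = 566.3

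| Medians (days) | Printed hazards | Power | Computed n | Table 7 |
|---|---|---|---|---|
| 38 vs 28 | 0.018, 0.025 | 90% | 200.3 | 201 |
| 32 vs 22 | 0.022, 0.032 | 90% | 155.3 | 156 |
| 63 vs 53 | 0.011, 0.013 | 90% | 758.6 | 759 |
| 63 vs 53 | 0.011, 0.013 | 80% | 566.3 | 567 |
| 20 vs 10 | 0.035, 0.0693 | 90% | 50.6 | 51 |

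Rounded up, all five entries match. One-sided 5% would give 618.5 and 446.2 for the two 63 versus 53 rows, which does not match.

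**Step 2: cases needed for 95% power, 63 versus 53.** With the printed hazards: (0.03326 + 1.6449 × 0.01703)² / 0.002² = 938.6, so 939 per group. With unrounded hazards (ln 2/63 = 0.011002, ln 2/53 = 0.013078): 877.2, so 878 per group. The text says 265.

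**Step 3: power at a given n.** Solve the formula for z_power:

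z_power = [√n × |λ₁ − λ₂| − 1.96 × √2 × λ̄] / √(λ₁² + λ₂²)

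| n per group | Printed hazards | Unrounded hazards |
|---|---|---|
| 265 | z = −0.04, power 48% | z = 0.02, power 51% |
| 450 | z = 0.54, power 70% | z = 0.62, power 73% |

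The log-rank event formula with 900 events agrees: 70.7% and 73.7%.

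**Step 4: what 450 per arm can detect from 63 days (unrounded hazards).** 80% power: 10.8 days. 90%: 12.3 days. 95%: 13.6 days.

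**Step 5: other baselines.** At 450 per arm, power for a 10-day reduction is 99.5% for 38 versus 28 (unrounded hazards) and over 99.9% for 32 versus 22 and 20 versus 10. It falls below 80% only when the routine median exceeds about 58.5 days.

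**The case against.** **The shortfall is specific and modest.** This stands. A reader might infer that the trial is underpowered for A1 in general. The documents do not support that: Table 7's other 10-day scenarios need 402, 312 and 102 cancers in total, far below 900, and a fall from 63 to 32 days, as in the earlier trial, would be detected with power over 99.9%. Even from 63 days, 450 per arm reaches 80% at a reduction of about 11 days.

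**The effect is expected to exceed 10 days.** The protocol says so, and it may be right. But the sentence states the 10-day case, and a larger hoped-for effect does not make that figure correct.

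**The 265 may be a correct result for other inputs.** Possible. The same formula at 95% gives 270 per group for 63 versus 46 days and 269 for 37 versus 27. A two-means calculation gives 265 if the SD is about 32 days, but the protocol gives no SD for this endpoint and Table 7's exponential model implies about 84–91. The origin of 265 cannot be settled from the document. What can be settled is that it does not fit 63 versus 53 days under Table 7's model.

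**Alpha is not stated.** True, and two-sided 5% is inferred from Table 7. At one-sided 5%, 265 per group would still give only about 61–63% and 900 cancers about 80–83%.

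**Two primary outcomes.** Section 4.2 says "Both outcomes will be considered primary and there are no hierarchy among these two", and a reader might infer that A1 must be tested at a stricter level, with lower power again. The document does not fix this. Section 7.3.1 calls time to CT co-primary, and handling of multiplicity is commonly left to a statistical analysis plan, which is not at hand. No such reduction is claimed here.

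**Conclusion.** The statement that 265 cases per group give 95% power for 63 versus 53 days is wrong as written and conflicts with Table 7, which is internally sound. For that comparison the true power is about 48–51% at 265 per group and about 70–73% at the 450 per arm expected; 95% would need about 880–940 per group. The unqualified assurance of ample power therefore does not hold at the 63-day baseline on which the text relies, although it does hold at Table 7's lower baselines.

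The 70–73% rests on two-sided 5%, exponential times, equal arms, independent patients and all 900 cancers being analysable events. Days rather than patients are randomised, and the study ends 12 months after first active deployment. Correlation of outcomes within days, or late cancers without a recorded diagnosis, would lower the figure; neither is quantified here.

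A reader might also infer that the trial must be enlarged. That does not follow: the error is in the stated power, and the design can stand with the power correctly described.

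**What to change.** In section 7.3.1:

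1. Remove the 265 per group/95% figure and reconcile the sentence with Table 7. If 265 came from another baseline or effect, give it with those inputs.
2. Change the reference from Table 6 to Table 7.
3. Replace the unqualified assurance of ample power with, for example: 'About 900 lung cancers (450 per arm) give about 70–73% power to detect a reduction in median time to diagnosis from 63 to 53 days, 80% power for a reduction of about 11 days and 90% for about 12 days. These figures assume a two-sided 5% test, exponential times, independent patients with no allowance for randomisation by day, and all 900 cancers analysable. For routine medians of 38 days or less, power for a 10-day reduction exceeds 90% (Table 7).'

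The cost is wording only. Sample size, sites and duration are unchanged; the stated power becomes less favourable.

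### Adequate power for the time-to-CT co-primary is claimed from all 4,000 primary-care CT chest scans, a count never reduced to scans that follow a suspicious chest X-ray, so the claim is not demonstrated

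*Protocol*

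**What the plan says.** Protocol section 4.2 makes time to diagnosis (A1) and time to CT (A2) both primary, without hierarchy, and restricts A2 to patients with suspected lung cancer. Section 7.3.1 (Part A) agrees: "The co-primary endpoint of this study is time between an abnormal CXR that is suspicious for lung cancer to CT chest".

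The same section then sizes A2 as follows.

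- Scan count, attributed to the NHS Diagnostic Imaging Dataset: "between 4,000-4,500 CT chest scans referred from primary care are expected during the study period at the clinical sites".
- Caveat, placed after the England median of 14 days from CT request to test: "this data is not segregated between urgent scans and those that are routine or for follow up".
- Mean and SD of the A2 time: stated to be unknown in both arms, so a standardised effect size is used.
- Allocation: "Assuming approximately equal distribution (Nnotification:Nstandard as 0.8 to 1.2) of the number of scans taken".
- Conclusion: "the estimated 4,000 CT chest scans will give adequate power to detect even the smallest effect size", with d = 0.1 as the smallest size.
- Target: "We have defined a clinically meaningful difference in time from abnormal to CT chest as 3 days".

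The text gives neither a numerical power nor a significance level for A2.

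**The concern.** The number put into the power statement is not a count of the A2 population. It is every CT chest scan referred from primary care, whatever the reason for the scan. A routine or follow-up CT need not come after a suspicious chest X-ray, and one that does not cannot contribute to A2. The protocol neither states what share of the 4,000 would qualify nor discounts the figure before concluding that power is adequate.

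The effect size is also left unconnected to the protocol's own target. A standardised difference of 0.1 corresponds to 3 days only at one particular SD, and the SD is stated to be unknown. A reader therefore cannot tell from the text how well the trial can detect the difference that it calls clinically meaningful. This is a positive statement about a co-primary outcome, so it should rest on the right count.

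**Working it through.** **Inputs from Protocol section 7.3.1:** N = 4,000 (upper end 4,500); d = 0.1; allocation ratio 0.8 to 1.2; target 3 days; SD unknown. **Assumed, because the section does not state it:** two-sided 5% level. The calculation compares two means by normal approximation, in line with the use of Cohen's d.

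**Step 1: reproduce the claim.** With total N split 1:1, power = Φ(d·√N/2 − 1.96).

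- N = 4,000: 0.1 × 63.25/2 = 3.162; 3.162 − 1.96 = 1.202; power 88.5%.
- Ratio 0.8: 88.2%. Ratio 1.2: 88.3%.
- N = 4,500, 1:1: 91.8%.

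The claim is reasonable if every scan counts towards A2.

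**Step 2: find the break-even count.** Total N for 80% power = 4(1.96 + 0.8416)²/d² = 4 × 7.849/0.01, or 3,140. That is 3,140/4,000 = 78.5% of the lower estimate, or 3,140/4,500 = 69.8% of the upper.

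**Step 3: vary the eligible share.** The documents do not give the share, so these rows are illustrations (d = 0.1, 1:1).

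| Eligible share of 4,000 | Eligible scans | Power |
|---|---|---|
| 100% | 4,000 | 88.5% |
| 90% | 3,600 | 85.1% |
| 80% | 3,200 | 80.7% |
| 75% | 3,000 | 78.2% |
| 50% | 2,000 | 60.9% |
| 25% | 1,000 | 35.2% |

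With 2,000 eligible scans, the effect detectable at 80% power is 2.8016 × √(4/2,000) = 0.125.

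**Step 4: relate this to the 3-day target.** d = 3/SD, so d = 0.1 means SD = 3/0.1 = 30 days. For 80% power, total N = 4 × 7.849 × (SD/3)², rounded up within each group. This gives 350 scans at an SD of 10 days, 684 at 14, 1,396 at 20 and 3,140 at 30. The SDs are assumptions.

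Power for 3 days, from the Step 1 formula with d = 3/SD:

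| Eligible scans | SD 10 (d = 0.30) | SD 20 (d = 0.15) | SD 30 (d = 0.10) |
|---|---|---|---|
| 1,000 | 99.7% | 66.0% | 35.2% |
| 2,000 | above 99.9% | 91.8% | 60.9% |
| 3,000 | above 99.9% | 98.4% | 78.2% |
| 4,000 | above 99.9% | 99.7% | 88.5% |

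For example, with SD 20 and N = 2,000: 0.15 × 44.72/2 = 3.354; 3.354 − 1.96 = 1.394; power 91.8%.

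**The case against.** A reader might infer that A2 is underpowered, or that the protocol itself calls the 4,000 wrong. The documents support neither.

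- **No shortfall is shown.** The stated arithmetic holds for 4,000 scans, and 80% power survives the loss of about a fifth of them. The eligible share is not given, so the lower rows of the table are possibilities, not findings.
- **The caveat may not concern the count.** The remark about unsegregated data directly follows the 14-day median and may refer to that alone. Count and median come in one sentence under one named dataset, so reading it as covering both is reasonable but not explicit. Even on the narrower reading, the count is described only as scans referred from primary care, which is not the A2 definition.
- **The A2 set need not be a subset of the 4,000.** Section 5 lets the reporting practitioner refer directly for CT and provides for recall after discordance review. Section 4.2 notes that some sites have respiratory review before CT. Some of these CTs might not be recorded as primary-care referrals, so the A2 count could exceed the eligible part of the 4,000, or even the 4,000 itself. This stands, and it also confirms that the 4,000 is not an A2 count.
- **The 3-day target partly favours the protocol.** For any SD below 30 days, 3 days is easier to detect than d = 0.1. This stands and limits the consequence.
- **Figure 2 could not be read.** It may show power by number of scans, so the point is confined to what the text claims.

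Two related points are not pressed. The endpoint is described as a difference in medians while Cohen's d concerns means, but no power loss from this has been quantified. The choice of test and any splitting of the significance level between the two primaries may properly sit in a statistical analysis plan.

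**Conclusion.** The point holds as a failure to demonstrate, not as proof of low power. The A2 power statement rests on a scan count wider than the endpoint's definition, with no eligible share stated and no reduction made. Under a two-sided 5% level, near-equal allocation and a comparison of means, the claim for d = 0.1 stands at 80% power or better only if at least 3,140 CTs qualify for A2. The wording about even the smallest effect size is therefore stronger than the text supports. Whether the 3-day difference is well powered depends on two quantities that the text does not give, the A2 count and the SD. It may well be, if the SD is clearly below 30 days.

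**What to change.** In section 7.3.1:

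1. Delete the wording about even the smallest effect size.
2. Estimate the number of A2-eligible CTs, meaning those that follow a chest X-ray suspicious for lung cancer by whatever referral route, from the eight sites' existing radiology data. State how the number was obtained.
3. Replace the d = 0.1 statement with a short table of power for the 3-day difference by eligible number (for example 1,000 to 4,000) and SD (for example 10, 20 and 30 days). State the significance level and allocation assumed.

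The cost is a count from data the sites already hold and a change of wording. No extra enrolment is needed. The downside is that the stated power for d = 0.1 may become less favourable; against that, the protocol would gain a direct justification for its own 3-day target, which may need far fewer scans.

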**Figure 2. Sample size calculation for time from abnormal CXR to CT chest (days)**

We would also like to have enough numbers to examine the secondary outcome if the strength of the agreement between qXR and CXR reporter in normal/abnormal classification. Based on an anticipated abnormal prevalence 40% of primary care CXRs and as measured by kappa (hypothesized as 0.82) an absolute precision of 2%, we would need 3,601 patients included. Not only is the time to diagnosis is important but also the accuracy of diagnosis. The study will also have enough number to report on agreement of individual abnormality with the above precision.

Table 7. Sample size calculation for time (in days) to diagnosis of lung cancer

	Median Days to diagnosis	Hazard	Sample Size	Total sample size	POWER
Routine	38	0.018	201	402	90
qXR immediate	28	0.025			
Routine	32	0.022	156	312	90
qXR immediate	22	0.032			
Routine	63	0.011	759	1518	90
qXR immediate	53	0.013			
Routine	63	0.011	567	1134	80
qXR immediate	53	0.013			
Routine	20	0.035	51	102	90
qXR immediate	10	0.0693			

#### Part B

No separate recruitment will be required for the health economic analysis

### 7.3.2 Sampling technique

#### Part A

A consecutive series of patients referred for CXR by primary care will be included.

Individual patients will not be randomised. Days will be randomised to intervention or standard care, using a randomisation list provided by the study statistician. This is in line with previous studies that have examined the timing or order of X-ray reading but where all examinations are requested as part of routine clinical care and receive reports from the same practitioners. No patient identifiable data will be available outside of the direct clinical care team. All data is routinely collected (mandatory reporting – cancer waiting times, service

SHORT TITLE/ACRONYM: LungIMPACT  
IRAS: 317009

evaluation – reporting times, radiology department activity, peer review) and will be anonymised prior to analysis.

Methodology of pseudo-anonymisation:

In accordance with data sharing and data processing practice, the transfer of DICOM files using Qure's API will be encrypted to prevent data breach. These DICOM files sent from each NHS site will be pseudo-anonymised before it leaves the hospital premise. This means all the patient identifiable data will be removed except for 'Patient ID' and 'Accession number'. These two IDs will be used as unique identifiers to map the AI outputs that would be sent back to the PACS/RIS after de-identification. It is also required to map with the corresponding cancer registry data that needs to be collected for realising the study objectives. Using these IDs would also help during discordance analysis, in case the expert radiologists wanted to check data history of the particular patient to help in decision making.

